18.12 Test Schedule Material(s)

CRF	Active-Monitoring Phase (Compliance with Test Schedule Section 4.0)	
	At each evaluation during treatment	At end of treatment
Evaluation/Treatment	X	X
Nadir/Adverse Event	X	X
Hematology Interval Laboratory	X	
Measurement	X	X
End of Active Treatment/Cancel Notification		X
ADR/AER	At each occurrence (see Section 10.0)	
SPEP, UPEP, FLC, Immunofixation, FISH, Cytogenetics, PCLI reports	X ²	X ²
Bone marrow biopsy report	X ¹	X ¹
Skeletal survey report	X ¹	X ¹
Stem Cell Harvest (optional)	X ³	

1. Only when required by the Test Schedule (see Section 4.0).
2. Submission of these reports is only required for documentation of CR (including sCR) or progression. For documentation of CR, submit all of these reports at the first confirmation of CR. For documentation of progression, submit one report for one of the measures where progression was seen. Submit reports to the QAS for MC138B.
3. May interrupt therapy for stem cell collection at any time per [Section 7.4](#). Submit the Stem Cell Harvest Form after stem cell collection has been completed.

18.13 Follow-up Material(s)

CRF	Event Monitoring Phase ¹				
	q. 6 months until PD ²	At PD ²	After PD q. 12 mos.	Death	New Primary
Event Monitoring	X	X	X	X	At each occurrence

1. If a patient is still alive 3 years after registration, no further follow-up is required.
2. Submit copy of documentation of response or progression to the MCCC Operations Office, Attention: QAS for MC138B.

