3.1 Inclusion Criteria

3.11 Age ≥ 18 years.

3.12 The following laboratory values obtained ≤ 7 days prior to registration.

- Absolute neutrophil count (ANC) $\geq 1700/\text{mm}^3$
- Platelet count $\geq 100,000/\text{mm}^3$
- Hemoglobin ≥ 8.0 g/dL
- SGOT (AST) ≤ 3 x upper limit of normal (ULN)
- Creatinine clearance ≥ 30 mL/min (as determined by Cockcroft-Gault equation*)

*Cockcroft-Gault Equations:

$$\text{Creatinine clearance for males} = \frac{(140 - \text{age})(\text{actual body weight in kg})}{(72)(\text{serum creatinine in mg/dL})}$$

$$\text{Creatinine clearance for females} = \frac{(140 - \text{age})(\text{actual body weight in kg})(0.85)}{(72)(\text{serum creatinine in mg/dL})}$$

Example: A woman aged 75, weight 50 kg and creatinine of 1.35 mg/dL has a calculated clearance of 28.

3.13 Diagnosis of multiple myeloma according to International Myeloma Working Group criteria and one of the following:

- SMM
- IMM
- newly diagnosed MM

Note: Patients with lytic disease and anemia are eligible

3.14 High risk disease defined by all of the following:

- $\geq 10\%$ bone marrow plasma cells
AND
- Abnormal serum free light chain (FLC) ratio (< 0.26 or > 1.65) by serum FLC assay
AND
- Monotypic Plasma Cell S-phase $\geq 0.3\%$

3.15 Measureable level of M-protein > 1 g/dL on serum protein electrophoresis or > 200 mg of M-protein on a 24 hour urine protein electrophoresis.

3.16 Negative tuberculosis (TB) testing (Quantiferon – TB blood test or skin test) ≤ 7 days prior to registration.

3.17 ECOG performance status (PS) 0, 1 or 2 ([Appendix I](#)).

- 3.18 Provide signed informed consent.
- 3.19a Negative (serum or urine) pregnancy test done ≤ 7 days prior to registration, for women of childbearing potential only.
NOTE: A second pregnancy test must be performed within 24 hours prior to the start of lenalidomide. The subject may not receive lenalidomide until the study doctor has verified that the results of these pregnancy tests are negative.
- 3.19b Willing to return to enrolling institution for follow-up (during the Active Monitoring Phase of the study).
- 3.19c Willing and able to comply with the requirements of the Revlimid REMS™ program.
- 3.19d Females of childbearing potential must be willing to adhere to the scheduled pregnancy testing as required by the Revlimid REMS™ program.
- 3.2 Exclusion Criteria
- 3.21 Prior treatment with any other agent that may affect M-protein ≤ 30 days prior to registration.

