4.0 Test Schedule

Tests and Procedures	Active Monitoring				
	≤7 Days Prior to Registration	End of Cycles 1-3 then end of every third cycle and end of treatment ⁷	Pre-treatment every cycle ⁵	Mid-cycle every cycle ¹⁰	End of Cycle 6 and Cycle 12, then yearly
Complete medical history	X				
Adverse Event monitoring	X	X ⁹	X		
Physical exam, including weight and vital signs	X	X			
Height	X				
Performance status (ECOG scale)	X	X			
EKG	X				
Hematology group (WBC, ANC, Hgb, PLT)	X	X ¹⁰	X ⁵	X	
Chemistry group (glucose, alkaline phosphatase; total bilirubin; SGOT (AST); serum creatinine, creatinine clearance, calcium, LDH and TSH ⁶)	X	X			
Beta ₂ -microglobulin, high sensitivity C-reactive protein	X	X			
SPEP and UPEP (24 hours collection)	X	X			
Circulating plasma cells (PBLI/PCLI)	X	X			
Immunofixation serum and urine	X ²	X ⁴			
Immunoglobulin free light chain (MML)	X	X			
Involved Immunoglobulin (IgA, IgG, IgM)	X	X ³			
X-ray skeletal survey (incl long bones) or low dose full body CT	X ²				X
Bone marrow aspirate and biopsy, myeloma FISH, metaphase cytogenetics, Plasma cell proliferation assay and flow cytometry	X ²	X ⁴			X
Serum or urine pregnancy test	X ¹	X ¹	X ^{1,5}		
Tuberculosis testing (Quantiferon blood test or skin testing)	X				
Register patient into Revlimid REMS® program	X				
Prescribe lenalidomide via Revlimid REMS		X ^{5,8}	X		
Research per IRB 521-93, optional ^R	X ^R				X ^R

- 1) Pregnancy tests for females of childbearing potential. A female of childbearing potential (FCBP) is a sexually mature female who: 1) has not undergone a hysterectomy or bilateral oophorectomy; or 2) has not been naturally postmenopausal for at least 24 consecutive months (i.e., has had menses at any time in the preceding 24 consecutive months). Pregnancy tests must occur ≤7 days prior to registration and again within 24 hours prior to initiation of lenalidomide. FCBP with regular or no menstruation must have a pregnancy test weekly for the first 4 weeks and then every 28 days while on therapy (including breaks in therapy); at discontinuation of lenalidomide and at Day 28 post the last dose of lenalidomide. Females with irregular menstruation must have a

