NOTE: If the patient experiences a significant adverse event requiring a dose reduction at the start of the next cycle, then the dose will remain lowered for that entire subsequent cycle. If that cycle is

completed with no further adverse events >Grade 2, then the dose may be increased, at the investigator's discretion, one level at a time, in the following cycles.

NOTE: Adverse events requiring a dose-reduction step for any or all drugs beyond the two dose-reduction steps (levels –1 and –2) will be at the discretion of the treating physician, if the decision is made for the patient to be kept on study. These dose reductions must be clearly recorded in reported clinical data.

NOTE: Patients in whom one or more of the study treatment agents have been discontinued will remain on study unless all study treatment agents are discontinued. Patients in whom all study treatment agents were discontinued will proceed to event monitoring (see [Section 18.0](#)).

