10.6 Required Routine Reporting

Adverse events to be graded at each evaluation and pretreatment symptoms/conditions to be evaluated at baseline per the CTCAE v4.0 grading unless otherwise stated in the table below:

SYSTEM ORGAN CLASS	Adverse event/Symptoms	Baseline	Each evaluation
Investigations	Creatinine increased	X	X
	Neutrophil count decreased	X	X
	Platelet count decreased	X	X
	Lymphocyte count decreased	X	X
	White blood cell decreased	X	X
	Anemia	X	X
General disorders and administration site conditions	Fatigue	X	X
	Injection site reaction		X
Gastrointestinal Disorders	Nausea	X	X
	Vomiting	X	X
	Diarrhea		X
	Constipation		X
	Number of stools	X	
Renal and urinary disorders	Chronic kidney disease (decreased creatinine clearance)	X	X
Skin and subcutaneous tissue disorders	Rash, maculopapular	X	X
Nervous system disorders	Peripheral sensory neuropathy	X	X
Constitutional Symptoms	Insomnia	X	X
Vascular Disorders	Thromboembolic event	X	X

10.61 Submit via appropriate MCCC Case Report Forms (i.e., paper or electronic, as applicable) the following AEs experienced by a patient and not specified in Section 10.6 (above):

10.611 Grade 2 AEs deemed *possibly, probably, or definitely* related to the study treatment or procedure.

10.612 Grade 3 and 4 AEs regardless of attribution to the study treatment or procedure.

10.613 Grade 5 AEs (Deaths)

10.6131 Any death within 30 days of the patient's last study treatment or procedure regardless of attribution to the study treatment or procedure.

- 10.6132 Any death more than 30 days after the patient's last study treatment or procedure that is felt to be at least possibly treatment related must also be submitted as a Grade 5 AE, with a CTCAE type and attribution assigned.
- 10.62 Refer to the instructions in the Forms Packet (or electronic data entry screens, as applicable) regarding the submission of late occurring AEs following completion of the Active Monitoring Phase (i.e., compliance with Test Schedule in [Section 4.0](#)).
- 10.7 All serious adverse events (SAEs) will be followed until resolution or death.

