16.11 Primary Endpoint

The primary endpoint of the phase I portion is toxicity, and more specifically, MTD determination. The primary endpoint of the phase II portion of this study is time to disease progression (TTP), which will be compared between the two arms. Time to progression is defined as the time from registration until the earliest date of documentation of disease progression. If a patient dies without a documentation of disease progression, the patient will be considered to have had disease progression at the time of their death unless there is sufficient documented evidence to conclude no progression occurred prior to death. If a patient receives subsequent treatment before disease progression, they will be censored on the date of the last disease assessment. All patients meeting the eligibility criteria who have signed a consent form and have begun treatment will be evaluable for the primary endpoint.

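### Once a phase II patient stops all treatment without progression, no disease test is scheduled, so ascertainment of TTP depends on whether the patient is still on treatment

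*Combined protocol and SAP*

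**What the plan says.** - **Endpoint (16.11).** "Time to progression is defined as the time from registration until the earliest date of documentation of disease progression". Stopping study treatment does not censor. New therapy does: "If a patient receives subsequent treatment before disease progression, they will be censored on the date of the last disease assessment". Death without documented progression counts as progression unless there is evidence otherwise.
- **What progression rests on (Table 11.5 and its footnotes).** Rises in serum or urine M-protein, new or larger bone lesions or plasmacytomas, or hypercalcemia, with two consecutive assessments normally required.
- **When the tests are done (4.0).** The table has a pre-registration column and Active Monitoring columns only. SPEP, UPEP and chemistry are due at "End of Cycles 1-3 then end of every third cycle and end of treatment". The skeletal survey is due at "End of Cycle 6 and Cycle 12, then yearly", also under Active Monitoring. Section 10.62 equates that phase with the Test Schedule ("completion of the Active Monitoring Phase (i.e., compliance with Test Schedule in"), and 3.19b asks for willingness to return only "during the Active Monitoring Phase of the study".
- **What happens after stopping.** The last note of Section 8 reads: "Patients in whom all study treatment agents were discontinued will proceed to event monitoring". Section 13.2 sends patients who withdraw early to the same place.
- **What event monitoring asks for (18.13).** An Event Monitoring form "q. 6 months until PD", a form at PD, and a copy of the documentation of response or progression. Footnote 1 ends follow-up 3 years after registration. The Measurement form appears only in 18.12, during and at the end of treatment.

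**The concern.** The endpoint definition needs progression to be looked for until it occurs, but the test schedule stops when treatment stops. Much of myeloma progression is a silent laboratory change, seen only if someone measures it, and normally measured twice. On treatment it is sought on a fixed calendar. Off treatment it is sought only as local care decides.

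Stopping treatment happens after randomization and may differ between anakinra and placebo, so blinding at entry does not equalize ascertainment. Progression that is found late or never documented favors the arm with more early stops. If new therapy starts before an unscheduled test shows progression, 16.11 censors the patient at the last disease assessment, which may be the end-of-treatment visit, and the event is lost. The sample size assumes negligible loss to follow-up and makes no allowance for this.

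**Working it through.** **1. The plan's own figure.** Inputs from 16.31: medians 20 and 40 months, one-sided 0.05, 80% power, 45 per arm, 24-month accrual, analysis at 52 progressions or 2 years after the last entry (about month 48).

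- Events (Schoenfeld): 4 × (1.645 + 0.842)² / (ln 2)² = 51.5, so 52.
- Power at 52 events: Φ(√52 × 0.693/2 − 1.645) = 0.80.
- Expected events by month 48, exponential TTP and uniform accrual: 31.7 + 20.7 = 52.4.

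The stated figures reproduce, with full ascertainment on and off treatment.

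**2. Share of progressions that occur off treatment.** The documents give no rate of stopping without progression, so I assume 15%-30% by 24 months.

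- Progression hazard h = ln 2/20 = 0.0347 or ln 2/40 = 0.0173 per month.
- Stopping hazard s = −ln(1 − p)/24 = 0.0068 (p = 0.15) or 0.0149 (p = 0.30).
- Follow-up t is uniform on 24 to 48 months.
- On-treatment progressions = 45 × h/(h + s) × mean[1 − exp(−(h + s)t)].
- All progressions = 45 × mean[1 − exp(−ht)].

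| Arm median | All | On treatment, p = 0.15 | On treatment, p = 0.30 | Off-treatment share |
|---|---|---|---|---|
| 20 months | 31.7 | 28.8 | 25.9 | 9%-18% |
| 40 months | 20.7 | 18.6 | 16.4 | 10%-21% |

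Here p is the rate that would be seen without competing progression. The share actually stopping without PD by month 24, s/(s + h) × [1 − exp(−24(s + h))], is 10%-21% (20-month arm) and 12%-25% (40-month arm). If 15%-30% is instead the share actually stopping, the off-treatment shares are 13%-26% and 12%-25%.

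**3. Later detection only.** Simulations took 12-week assessment on treatment and detection at each 6-monthly form off treatment, with more stopping in the experimental arm. One-sided error under the null was 0.048-0.064, against 0.046-0.056 with 12-week assessment throughout. Matched differences were 0 to 0.008, with simulation error of about 0.004-0.005 on each figure. That is no clear effect.

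**4. Progression never documented, type I error.** Null simulation with 20-month medians, half of off-treatment progressions missed, and those patients carried as progression-free:

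- 15% vs 30% stopping (control vs experimental): about 0.07-0.08.
- 15% vs 45%: about 0.12.
- Equal stopping: no clear inflation.

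The handling matters. When every off-treatment progression was missed but patients were censored at stopping (20% vs 40%), error was 0.049. The inflation comes from counting untested patients as progression-free.

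**5. Progression never documented, power.** All off-treatment progressions missed, equal stopping in both arms, month-48 cutoff: 20% gives 45.7 events and power 0.76; 30% gives 42.3 events and power 0.73.

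**6. The 3-year limit.** At a month-48 analysis, anyone registered in the first 12 of the 24 accrual months (48 − 36 = 12) has passed 3 years. If the limit applied to every patient, expected events would be 50.1 and power 0.79. This is an upper bound on its effect, since the footnote sits under event monitoring.

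**7. Who reaches event monitoring.** The Section 8 note keeps patients on study when one agent is stopped, so assessments continue. The footnote to the anakinra table in 8.1 sends patients who cannot tolerate level −2 off treatment to event monitoring. Differential stopping between arms depends on which applies. These passages must be reconciled.

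**The case against.** The strongest reply is that the plan does collect progression off treatment. Section 18.13 has the 6-monthly form, the form at PD and the documentation copy; 16.11 does not censor at stopping, and unexplained deaths count by default. All of that stands. A reader might infer from the test schedule that TTP is measured on treatment only. The documents do not support that: an off-treatment progression that is found and reported counts.

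A second reply is that the numbers are small. It stands for delay, which has no clear effect on type I error. A reader might also take s/(s + h) as the off-treatment share, which gives 16%-30% and 28%-46%. Those figures assume unlimited follow-up; 16.31 ends the trial at about month 48, and the shares are then as in the table above.

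A third reply is that stopping anakinra or placebo alone keeps a patient on scheduled assessments. The Section 8 note says so, but the 8.1 footnote points the other way, so the reply cannot be relied on until they agree.

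What survives is narrower: testing off treatment is unscheduled and not standardized, and nothing in the plan limits how much progression goes undocumented.

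**Conclusion.** The gap is real and concerns the primary endpoint. Followed as written, the plan seeks progression on a fixed calendar on treatment and by unscheduled testing off it.

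Its size is uncertain because the stopping rate, the difference between arms and the share undocumented are all assumptions. About 9%-21% of progressions are exposed under a rate equivalent to 15%-30% stopping by 24 months, or 12%-26% if that is the share actually stopping without PD. Material type I inflation, about 0.07-0.08 to 0.12 in the cases tried, needs both unequal stopping and undocumented progression in patients carried as progression-free. Power loss needs only missed progression. The sample-size arithmetic itself is sound. This is a low-cost improvement that should be made, not evidence that the comparison is biased. It applies to phase II; Addendum 5 ended event monitoring for phase I only.

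**What to change.** - In 4.0 and 18.13, for phase II patients who stop all study treatment without PD, add SPEP, 24-hour UPEP where urine is followed, and calcium every 12 weeks by calendar from registration. Require the Measurement form each time. Continue until PD, new anti-myeloma therapy or the final analysis. Accept mail-in or local samples, as footnotes 4, 5 and 10 of Section 4.0 already do for some tests.
- Amend 18.13 footnote 1 so that follow-up for progression does not end at 3 years if the final analysis is later.
- State whether the yearly skeletal survey continues off treatment. It is now scheduled only under Active Monitoring, so continuing it would be a new requirement.
- Reconcile the 8.1 footnote with the Section 8 note on who moves to event monitoring.
- Add a sensitivity analysis for off-treatment ascertainment, for example censoring at the last disease assessment.

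Cost: a protocol amendment, some routine tests and forms in the patients who stop early, and some refusals among those who withdrew.

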2.2 Secondary Objectives

2.21 To compare the response rate of the standard treatment arm (lenalidomide/dexamethasone) to the experimental arm (lenalidomide/dexamethasone + anakinra).

2.22 To compare the toxicity of the standard treatment arm (lenalidomide/dexamethasone) to the experimental arm (lenalidomide/dexamethasone + anakinra).

2.23 To compare the overall survival of the standard treatment arm (lenalidomide/dexamethasone) to the experimental arm (lenalidomide/dexamethasone + anakinra).

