13.0 Treatment/Follow-up Decision at Evaluation of Patient

NOTE (Phase I Only): As of Addendum 5, Anakinra will no longer be provided and all patients will go off study treatment. Event monitoring will no longer be required. Patients may obtain Anakinra commercially and be treated off study

- 13.1 Responding to treatment
Patients who are sCR, CR, VGPR, PR, or SD (or usCR, uCR, uVGPR, uPR) will continue treatment per protocol.
- 13.2 Treatment continuation
In the absence of treatment delays due to adverse event(s), treatment may continue until one of the following criteria applies:
 - 13.21 Progression requiring treatment for active myeloma
 - 13.22 Unacceptable toxicity and ineligibility for retreatment.
 - 13.23 Patient refusal of continued treatment.

All attempts should be made to complete the End of Study procedures if a patient withdraws from the trial early. The patient will then go to event monitoring per Section 18.0.

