16.13 Accrual Rate and Study Duration

The anticipated accrual rate is 4 patients per month assuming that approximately one third of newly diagnosed patients will be high risk. At this rate, it will likely take about 2.5 months to enroll, treat, and evaluate each cohort in the phase I portion of this study. The phase I portion is expected to take between 10 and 15 months. The phase II portion of this study is expected to accrue in 2 years. The total study duration is expected to be approximately 5.5 years, or until the last patient accrued has been observed for at least 2 years.

Phase I Portion

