The primary goal of this trial is to compare the time to progression of the standard treatment arm (Arm A) to the experimental arm (Arm B). We will conduct a randomized trial comparing the experimental arm against the standard treatment arm. We will enter 45 evaluable patients to each arm of the study using a 1:1 randomization scheme (Pocock et al, 1975). The stratification factors that will be used are listed in Section 5.0. The primary analysis will be a comparison of Arm A to Arm B using a one-sided log-rank test between the two Kaplan-Meier curves. This final analysis will take place after an approximate 24-month accrual period and after 52 total progressions have occurred or the last patient has been followed for at least 2 years (whichever occurs first). Additionally, we assume a constant accrual rate over the course of the study and that we will not have a significant lost to follow-up issue, as historically lost to follow-up rates in Mayo clinic trials have been $< 1\%$. A sample size of 45 evaluable patients per arm (90 total) provides 80% power to detect an improvement in median time to progression from 20 months to 40 months (a hazard ratio of 2.0), using a 1-sided log-rank test at a significance level of 0.05. A final decision regarding the level

of promise for the experimental regimen will take all factors into account including TTP, response rate, OS, adverse events, and other relevant factors. All patients meeting the eligibility criteria who have signed a consent form and have begun treatment will be evaluable for the primary endpoint.

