16.33 Secondary Outcome Analyses

The secondary endpoints listed below will be evaluated in each arm independently and will also be compared between the two arms in an exploratory manner.

16.331 Survival time is defined as the time from registration to death due to any cause. The distribution of survival time will be estimated using the method of Kaplan-Meier within each arm and compared between the arms using a one-sided log-rank test.

16.332 Overall response rate: The overall response rate will be estimated by the number of patients with an objective status of sCR, CR, VGPR, or PR divided by the total number of evaluable patients. All evaluable patients will be used for this analysis. Exact binomial 95% confidence intervals for the true overall response rate will be calculated within each arm and compared between the arms using Fisher's exact test.

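### Required follow-up of patients off treatment stops at 3 years, up to a year before the latest phase II final analysis, so late overall survival data depend on treatment status

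*Combined protocol and SAP*

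**What the plan says.** Section 18.13, footnote 1 to the Event Monitoring Phase: "If a patient is still alive 3 years after registration, no further follow-up is required".

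Who is in that phase is set elsewhere. The notes that close Section 8 say "Patients in whom all study treatment agents were discontinued will proceed to event monitoring". Patients still on drug remain on the Section 4.0 schedule ("End of Cycles 1-3 then end of every third cycle and end of treatment"). Section 13.2 sets no maximum duration of treatment; it ends for toxicity, refusal or "Progression requiring treatment for active myeloma".

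On timing, Section 16.13 says "The phase II portion of this study is expected to accrue in 2 years". Section 16.31 places the final analysis after "52 total progressions have occurred or the last patient has been followed for at least 2 years (whichever occurs first").

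On the endpoint, Section 2.23 sets out "To compare the overall survival of the standard treatment arm" with that of the experimental arm. Section 16.331 says "Survival time is defined as the time from registration to death due to any cause", estimated by Kaplan-Meier and compared by a one-sided log-rank test. Section 16.33 calls the between-arm comparison exploratory.

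**The concern.** A common cut-off at 36 months would do no harm. This one is not common to all patients. Beyond month 36, survival must still be recorded for patients on drug, but not for those who have stopped every agent. Patients stop largely because they progress, and patients who have progressed die sooner. The required risk set after month 36 is thus selected for good prognosis. If anakinra delays progression, the selection also differs by arm.

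At stake is the late part of the OS curves, a stated secondary objective and one of the factors that Section 16.31 lists for judging the promise of the regimen. Section 16.31 relies on loss to follow-up below 1%, but that concerns unplanned loss, not a scheduled stop. Outside event monitoring, Sections 10.52 and 10.613 capture deaths within 30 days of the last dose and, later, only those at least possibly related to treatment. The Addendum 5 note that ends event monitoring is marked as phase I only, so it does not settle the matter for phase II.

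**Working it through.** **Inputs from the plan (16.13, 16.31, 18.13).** 45 patients per arm, 1:1; median TTP 20 vs 40 months, exponential; one-sided 0.05; accrual 24 months, taken as uniform; analysis at the earlier of 52 events and 24 months after the last registration; event monitoring to month 36.

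**Assumptions (not in the plan).** Median survival after progression 36 months (range 24 to 60); no deaths before progression; treatment ends at progression.

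**1. The plan's own figure.** Schoenfeld events = 4(1.645 + 0.842)² / (ln 2)² = 51.5, so 52; power with 52 events is 80.4%. The stated 52 and 80% are reproduced.

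**2. Size of the gap.** Latest analysis: 24 + 24 = month 48, and 48 − 36 = 12 months. Expected events at month 48 are 52.4. In 6,000 simulated trials the mean cut-off is about month 45.6. Patients past month 36: 90 × 12/24 = 45 at month 48, or about 36 at the mean cut-off (90 × 9.5/24 = 35.6 at month 45.5).

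**3. Who stays under required follow-up.** Progression-free at month 36: 2^(−36/20) = 28.7% in control and 2^(−36/40) = 53.6% with anakinra.

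**4. Bias in OS.** With a = ln 2 / (TTP median) and b = ln 2 / (post-progression median), S(t) = [b·exp(−at) − a·exp(−bt)] / (b − a). Under the assumptions no death after month 36 has to be collected, so the required Kaplan-Meier curve is flat from there. The bias at month 42 is S(36) − S(42).

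| Post-progression median | Control | Anakinra | Difference |
|---|---|---|---|
| 24 months | 6.8 points | 4.8 points | 2.0 |
| 36 months | 0.766 − 0.711 = 5.5 points | 0.859 − 0.821 = 3.8 points | 1.7 |
| 60 months | 3.9 points | 2.7 points | 1.2 |

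Simulation at 36 months gives 5.4 and 3.7 points. Mean numbers at risk at month 42 are 5.2 (control) and 6.0 (anakinra) with full follow-up, and 1.8 and 3.7 under the footnote. The SDs of the estimates are 9.5 and 8.1 points, so the SD of the difference is √(9.5² + 8.1²) = 12.5 points. The between-arm bias is 1.7/12.5 = 0.14 SD.

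**5. Deaths that need not be collected (simulated).** In the base case, 15.1 − 13.7 = 1.4, with at least one in about 70% of trials. For post-progression medians of 24 and 60 months: 1.7 of 20.5 and 1.0 of 10.0.

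| TTP medians (months) | Mean cut-off (month) | Deaths uncollected |
|---|---|---|
| 20 vs 40 | 45.6 | 1.4 |
| 20 vs 30 | 42.5 | 0.8 |
| 20 vs 25 | 40.3 | 0.5 |
| 20 vs 20 | 37.5 | 0.2 |

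**6. Relaxing the other assumptions (medians 20 vs 40).**
- If 25% or 50% of progressed patients stay on treatment, 1.0 or 0.7 deaths are uncollected. The bias is 2.7 or 1.5 points (control) and 2.3 or 1.4 points (anakinra).
- If 5% or 10% die before progression by month 36, 1.1 or 0.8 deaths are uncollected. The bias is 4.7 or 4.6 points and 3.3 or 2.7 points.

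**7. TTP.** Only patients who stopped all drugs without progressing are affected. If 10% to 50% of unprogressed patients are off drug by month 36 (assumption), 0.3 to 1.2 of 52.4 events are lost at month 48. Power moves from 80.6% to between 80.5% and 79.8%. Capping every patient at 36 months, an extreme, leaves 50.1 events and 79.0%.

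**The case against.** The case for leaving the footnote alone has several sound parts. A fixed 3-year horizon is an ordinary use of resources, and the footnote says what is not required; it does not forbid later collection. OS is exploratory. The base case is close to the worst in effect size, because weaker effects bring the 52nd event forward. It also forces the bias by ending all treatment at progression, whereas 13.21 stops treatment only for progression that needs therapy for active myeloma, and smoldering and indolent patients are eligible. With half of progressed patients still on drug, the bias is about equal in the two arms. Few patients are at risk at month 42 in any case. All of this stands and limits the size of the point. None of it removes the mismatch between OS without a time limit and follow-up that depends on treatment status.

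One apparent remedy would do harm. If follow-up simply ran to the final analysis, about 54 of 90 patients, now owed 36 months, would have less at that date. In the base case 15.2 deaths would be collected, against 16.9 if the footnote is followed to its end.

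A reader might infer that the primary analysis is damaged or that the footnote could create a false survival benefit for anakinra. The documents do not support either. TTP power hardly moves (step 7). Under the planning assumptions the overstatement is larger in control, so it works against anakinra. If the arms do not differ in progression, treatment duration or survival, the selection acts alike in both.

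**Conclusion.** The point holds as a small defect that is cheap to remove. From month 36, required OS follow-up depends on whether a patient is still on treatment, while the OS definition and analysis assume follow-up to death or data cut-off. Under the planning medians and the stated assumptions, about 1.4 of 15 deaths go uncollected and late OS is overstated by about 5 points (control) and 4 points (anakinra), about 2 points between arms. These figures are near the upper end for effect size. The plan states no phase II assumption for survival after progression or for time on treatment after it, so the sizes are conditional; the mismatch in the text is not.

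**What to change.** For phase II, replace footnote 1 in 18.13 with: *Follow every patient, on or off treatment, for progression and survival until death or the later of 3 years after registration and the phase II final analysis.* The later-of wording keeps the 36 months already owed to later registrants.

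The cost falls on at most about 45 early registrants (about 36 at the mean simulated cut-off). Each needs up to two extra 6-monthly contacts before progression, or one yearly contact after it, on the existing Event Monitoring form. Sample size, analysis timing and the 5.5-year duration do not change.

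If no extra contacts are wanted, state in 16.331 that OS is censored at 36 months from registration in all patients in both arms. That needs one sentence and no new data; the price is the few deaths after month 36.
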